Management of infusion reactions: refer to institutional policy; see section 6.4 for additional guidance. Steroids should be avoided as a routine premedication due to possible interference with the efficacy of the study agents. Pre-medications are not required but are allowed for patients with previous infusion reaction.

Treatment Period.

The treatment period of the induction phase is Day 1-84 (12 weeks).

The treatment period of the maintenance phase is from Day 85 to 337 (36 weeks). Day

337 is the last protocol-directed infusion of nivolumab (see below) and the last dose of troriluzole.

Adherence/Compliance. At the visit, each subject will be given a bottle containing capsules of study drug. The participant will be requested to maintain a medication diary of each dose of medication. The medication diary will be returned to clinic staff at the end of each cycle. Unused study medication will be returned to the research pharmacy. At the end of each cycle of treatment, the actual amount of unused drug will be compared to the amount taken as recorded on the subject's medication diary. The desired level of compliance is >75%. If a subject is below that threshold, the treating investigator should assess barriers to compliance and address any correctable barriers (e.g. antiemetic therapy). Patients who cannot maintain this level of compliance may be removed from the study at the discretion of the treating investigator.

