5.10 Criteria for Taking a Participant Off Study

Safety Run-In and Randomized Treatment:

Participants will be removed from study (including study follow-up) when any of the following criteria apply:

- Lost to follow-up
- Withdrawal of consent for data submission
- Death

The reason for taking a participant off study, and the date the participant was removed, must be documented in the case report form (CRF). In addition, the study team will ensure the participant's status is updated in OnCore in accordance with [REGIST-OP-1](#).

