6. DOSING DELAYS/DOSE MODIFICATIONS

6.1 General considerations

The descriptions and grading scales found in the revised NCI Common Terminology Criteria for Adverse Events (CTCAE) version 5.0 will be utilized for dose delays and dose modifications. A copy of the CTCAE version 5.0 can be downloaded from the CTEP website http://ctep.cancer.gov/protocolDevelopment/electronic_applications/ctc.htm.

Dosing interruptions are permitted in the case of medical / surgical events or logistical reasons not related to study therapy (e.g., elective surgery, unrelated medical events, patient vacation, and/or holidays) and do not constitute a protocol violation. Subjects should be placed back on study therapy within 4 weeks of the missed dose, unless otherwise discussed with the study PI. The reason for interruption should be documented in the patient's study record. The maximum dose interruption of the checkpoint inhibitors (no administrations) for any reason is 84 calendar days (12 weeks). The maximum dose interruption of the Troriluzole for any reason is 42 calendar days (6 weeks). Missed doses are not to be made up; efforts will be made to get the patient back on the original schedule so that assessments are uniform across subjects.

For AEs unrelated to study drug(s), therapy may be held/resumed at the discretion of the treating investigator. Treatment-emergent AEs should continue to be monitored during the follow-up period (until resolution). New AEs during follow up that are not related to treatment should not be recorded

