6.3 Troriluzole

General

Troriluzole therapy will be continued if there is an interruption in checkpoint therapy due to AE, and the AE is unlikely related or unrelated to troriluzole. Troriluzole and corticosteroids can be taken concurrently. Nivolumab and/or ipilimumab may still be given if Troriluzole is held or discontinued, if AE is unlikely related or unrelated to the checkpoint inhibitor treatments.

The maximum amount of time that troriluzole can be held continuously is 6 weeks. If the patient cannot resume troriluzole within 6 weeks, the patient will be removed from the study.

If a participant experiences multiple adverse events and there are conflicting recommendations, the investigator should use the recommended dose adjustment that reduces the dose to the lowest level.

Holding criteria

Troriluzole vs. placebo will be omitted and dose reduced for related AEs as follows.

Grade 1

For grade 1 events, dose holding is not required. If the grade 1 toxicity is intolerable to the patient, the drug may be held for 1 week at a time without lowering the dose. If drug is held for >1 week at a time, drug will be dose-reduced **one** level upon resumption. The intolerable nature of the AE must be documented as the reason for holding drug.

Grade 2

For grade 2 events, dose holding is required. When troriluzole is interrupted for an AE, the toxicity should be continually reassessed until it improves to Grade ≤ 1 , on approximately a weekly basis, which can be done remotely by telephone and/or lab assessment. If patient is able to resume drug ≤ 1 week, drug will be continued at the same dose, or, at the discretion of the treating investigator, it may be dose-reduced. If drug is held for >1 week at a time, it should be dose-reduced one level upon resumption. If grade 2 AE meets criteria for DLT (see section 6.2), troriluzole should be dose-reduced one level upon resumption.

Grade 3

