For grade 3 events, dose holding is required. When troriluzole is interrupted for an AE, the toxicity should be continually reassessed until it improves to Grade ≤ 1 , on approximately a weekly basis, which can be done remotely by telephone and/or lab assessment. If the treating investigator believes permanent discontinuation is in the best interest of the patient (e.g. anaphylaxis), Troriluzole may be permanently discontinued after a discussion between the treating investigator and principal investigator. If the patient is able to resume drug, drug will be dose-reduced **one level**.

Grade 4

For grade 4 events, dose holding is required. When troriluzole is interrupted for an AE, the toxicity should be continually reassessed until it improves to Grade ≤ 1 , on approximately a weekly basis, which can be done remotely by telephone and/or lab assessment. If the treating investigator believes permanent discontinuation is in the best interest of the patient (e.g. anaphylaxis), troriluzole may be permanently discontinued after a discussion between the treating investigator and principal investigator. If the patient is able to resume drug, drug will be dose-reduced **two levels**.

Troriluzole vs. Placebo Dose Reductions

No specific management is indicated when troriluzole vs. placebo is held, other than supportive care. When therapy resumes, the dose must be reduced by one level per the table below. The maximum number of dose reductions is 2 as shown in the following de-escalation table.

Dose reductions for troriluzole

Dose Level	Troriluzole vs. Placebo Dose
0	140 mg PO QAM and 280 mg PO QPM
-1	140 mg PO BID
-2	140 mg PO daily

Intra-participant dose reescalation. Intra-participant dose reescalation is allowed. At the discretion of the treating physician, a patient who has previously been dose-reduced may re-escalate up to the starting dose. No patient should take more than the starting dose (Cohort 0). For example, if a AE improves with additional supportive measures (antiemetics, etc), or an alternate cause of the AE is identified, the physician and patient may opt to re-escalate.

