Maximum delay: The maximum amount of time that checkpoint inhibitor(s) can be held continuously is 12 weeks. If the patient cannot resume therapy within 12 weeks, the patient will

be removed from treatment with checkpoint inhibitor.

Patients requiring a delay of > 12 weeks due to ongoing immune-related toxicity or inability to taper prednisone to ≤ 10 mg PO daily (dexamethasone ≤ 1.5 mg PO daily) must go off checkpoint inhibitor therapy entirely.

Table 6.1 Dose Modification for Related Adverse Events

Treatment-related Adverse Event	Grade of Event	Nivolumab or Nivolumab/Ipilimumab
Nausea	\leq Grade 1	No dose modification
	Grade 2	Hold until \leq Grade 1 OR baseline (exceptions as noted below) ¹
	Grade 3	Off nivolumab and/or ipilimumab treatment (exceptions as noted below) ¹
	Grade 4	Off nivolumab and/or ipilimumab treatment
Recommended management: antiemetics.		
Diarrhea (immune-related enterocolitis)	\leq Grade 1	No dose modification
	Grade 2	Hold until \leq Grade 1 OR baseline
	Grade 3	Off nivolumab and/or ipilimumab treatment (exceptions as noted below) ¹
	Grade 4	Off nivolumab and/or ipilimumab treatment
Recommended management: Loperamide antidiarrheal therapy Dosage schedule: 4 mg at first onset, followed by 2 mg with each loose motion until diarrhea-free for 12 hours (maximum dosage: 16 mg/24 hours) Adjunct anti-diarrheal therapy is permitted and should be recorded when used. Please evaluate pituitary function prior to starting steroids if possible without compromising acute care. Evaluation for all patients for additional causes includes C. diff , acute and self-limited infectious and foodborne illness, ischemic bowel, diverticulitis, and IBD.		
Vomiting	\leq Grade 1	No dose modification
	Grade 2	Hold until \leq Grade 1 OR baseline (exceptions as noted below) ¹
	Grade 3	Off nivolumab and/or ipilimumab treatment (exceptions as noted below) ¹
	Grade 4	Off nivolumab and/or ipilimumab treatment
Recommended management: antiemetics.		
Other GI	\leq Grade 1	No dose modification
	Grade 2	Hold until \leq Grade 1 OR baseline (exceptions as noted below) ¹
	Grade 3	Off nivolumab and/or ipilimumab treatment (exceptions as noted below) ¹
	Grade 4	Off nivolumab and/or ipilimumab treatment
Patients with Grade 2 or 3 N-V should be evaluated for upper GI inflammation and other immune related events.		
Neurologic	\leq Grade 1	No dose modification

Treatment-related Adverse Event	Grade of Event	Nivolumab or Nivolumab/Ipilimumab

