13.7 Reporting and Exclusions

Evaluation of Toxicity

All participants will be evaluable for toxicity from the time of their first treatment.

Evaluation of the Primary Efficacy Endpoint

The analysis of the primary endpoint will be conducted using the intention-to-treat principal, meaning all randomized patients will be evaluated according to the treatment assigned at the time of enrollment.

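### Section 6.3 makes a troriluzole/placebo interruption of more than 6 weeks a reason to leave the study, which conflicts with the off-study list in 5.10 and could cut primary-endpoint follow-up short

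*Combined protocol and SAP*

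**What the plan says.** Section 6.3 (General) sets the rule for a long hold of troriluzole or placebo: "If the patient cannot resume troriluzole within 6 weeks, the patient will be removed from the study". Section 6.1 applies the same 42-day limit whatever the cause of the interruption.

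Section 5.10 gives leaving the study a defined meaning: "Participants will be removed from study (including study follow-up) when any of the following criteria apply". Its list has three entries: loss to follow-up, withdrawal of consent for data submission, and death. Coming off protocol therapy is a separate status with its own list in Section 5.8. That list includes unacceptable adverse events and failure to comply with the oral regimen.

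Other passages also separate stopping a drug from leaving the study:

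- Section 6.3 says that "Nivolumab and/or ipilimumab may still be given if Troriluzole is held or discontinued", provided the adverse event is not attributed to the checkpoint inhibitors.
- For severe events, Section 6.3 says that "Troriluzole may be permanently discontinued after a discussion between the treating investigator and principal investigator", and does not mention leaving the study.
- Under Section 6.4, a patient who cannot restart checkpoint inhibitors within 12 weeks will "be removed from treatment with checkpoint inhibitor".
- Section 5.4 and Study Calendar footnote i provide for in-person visits after early discontinuation.

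Section 5.3 repeats the 6.3 wording for poor adherence, in permissive form: "Patients who cannot maintain this level of compliance may be removed from the study at the discretion of the treating investigator".

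The primary analysis in Section 13.7 is by intention to treat, "meaning all randomized patients will be evaluated according to the treatment assigned at the time of enrollment". A patient without a PFS event is censored at the last follow-up visit (13.1) or the last disease evaluation (11.5).

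**The concern.** Section 6.3 is mandatory and uses the term that 5.10 defines as ending follow-up. Applied literally, a randomized patient who is alive and progression-free, and perhaps still receiving nivolumab, would have data collection stopped because the blinded capsule was not resumed. Global PFS would then be censored near the time of stopping. Overall survival would be censored too if the site also disregarded the survival contacts in 5.9 and footnote j.

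Holding is required for related grade 2 to 4 events, so this censoring would often follow from tolerability. It could therefore be associated with both treatment and prognosis, whereas the planned analysis treats censoring as uninformative. The proportional hazards mixture cure model in 13.5 is exposed because its cure fractions are estimated from long follow-up, which early removal takes away. With at most 90 randomized patients, a modest number of such cases matters, and outcomes that were never collected cannot be recovered at analysis.

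**Working it through.** **1. The texts side by side**

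| Situation | Consequence stated | Section |
|---|---|---|
| Troriluzole/placebo not resumed within 6 weeks | Leaves the study | 6.3 |
| Troriluzole permanently stopped for a severe event | Stops troriluzole; nothing on leaving the study | 6.3 |
| Checkpoint inhibitor not resumed within 12 weeks | Leaves that treatment only | 6.4 |
| Oral non-compliance | Leaves protocol therapy | 5.8 |
| Oral non-compliance | May leave the study | 5.3 |
| Leaving the study | Ends follow-up; three listed reasons, none of them the above | 5.10 |

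The same kind of event has different consequences in different places, and no sentence sets an order of precedence.

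**2. Would the favourable reading secure the PFS data?** Footnote i asks for evaluation in person every 84 days until five follow-up visits are done, but names no scans. The calendar marks brain MRI at Day 43, and MRI and CT at Days 85, 169, 253 and end of treatment. It marks neither in any follow-up column. Section 5.9 leaves imaging on Days 421 to 589 to standard of care. A patient who ends treatment early therefore has no mandated scan afterwards, even before month 6.

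**3. The plan's own design figures (13.2)**

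- Cure odds ratio: (0.5/0.5)/(0.3/0.7) = 2.33, as stated.
- Uncured hazard λ: 0.3 + 0.7·exp(−6λ) = 0.6 gives λ = 0.141 per month.
- INT 6-month PFS: 0.5 + 0.5·exp(−6 × 0.141 × 0.557) = 0.81, against about 0.8 stated.

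The sample size of 90 is not in dispute here.

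**4. Possible size.** The documents give no rate for holds beyond 6 weeks. The nearest anchors are about 14% discontinuation for adverse events in chronic riluzole trials (7.1) and dose-limiting toxicity in 3 of 14 phase Ib patients (2.4). All removal rates below are assumptions.

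The simulation used 45 patients per arm, the design values above, 24 months of accrual plus 12 of follow-up, and removal times uniform over 1.5 to 6 months. It used a log-rank test, not the planned cure model. There were 4,000 runs per row (6,000 for power with no removal), so the simulation error is about 0.005. Section 13.2 does not say whether alpha 0.1 is one- or two-sided, so both are shown. Under the null, both arms have a 30% cure fraction and the same hazard. In the partly concentrated setting, cured patients have half the removal probability. In the fully concentrated setting, only uncured patients are removed. The arm's overall rate is kept in both.

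| Removal INT/INP | Power, two-sided 0.1, removal unrelated to prognosis | False positives for INT, nominal 0.05, partly / fully concentrated | Same, nominal 0.10 |
|---|---|---|---|
| none | 0.851 | 0.052 | 0.105 |
| 5%/2% | 0.851 | not run | not run |
| 10%/5% | 0.826 | 0.056 / 0.063 | 0.115 / 0.114 |
| 14%/5% | 0.821 | 0.063 / 0.079 | 0.120 / 0.142 |
| 14%/14% | 0.810 | not run | not run |
| 25%/10% | 0.802 | 0.069 / 0.092 | 0.130 / 0.168 |

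In the concentrated null cases at 14%/5% and 25%/10%, the mean gap in estimated 6-month PFS was 0.4 to 1.4 points (for example 0.621 − 0.607 = 0.014), where the true gap is zero.

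**5. Direction.** Assume a true 6-month PFS of 0.60 and a fraction w of the arm due for removal at month 3 if event-free. Assume 3-month PFS of 0.70 in that group and 0.81 in the rest, and 6-month PFS of q in that group. The censored estimate is S(3) × S_rest(6)/0.81, with S(3) = 0.81(1−w) + 0.70w and S_rest(6) = (0.60 − wq)/(1−w).

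- w = 0.15, q = 0.30: 0.7935 × 0.653/0.81 = 0.640.
- w = 0.10, q = 0.30: 0.799 × 0.633/0.81 = 0.625.
- w = 0.15, q = 0.65: 0.7935 × 0.591/0.81 = 0.579.

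If the first case is INT and the second INP, the false gain is 0.640 − 0.625 = 1.5 points. In the third case the sign reverses.

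**The case against.** The best defence is that the wording in 6.3 is a slip that the rest of the plan corrects. Section 5.8 already treats adverse events and oral non-compliance as reasons to leave therapy, 5.10 does not list them, and 5.4 and footnote i describe visits after early discontinuation. Section 5.9 and footnote j collect survival for 3 years and do not exempt patients who are off troriluzole. Part II is double-blind, and Section 6.7 says that shared adverse events should in most cases be attributed to all three drugs. Checkpoint toxicity will therefore cause capsule holds on placebo as well, which narrows any difference between arms. The 6.1 limit also covers interruptions that have nothing to do with toxicity.

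Much of this stands. It shows that sites could reasonably continue follow-up, and that 5.3, being permissive and answered by 5.8, is only secondary support. It does not remove the conflict, because 6.3 remains mandatory and uses the term that 5.10 defines. Nor do the passages relied on require scans after treatment ends early.

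A reader might go further and infer that the intention-to-treat analysis is defeated. The documents do not support that: removed patients are still analysed as assigned, and what is lost is their later outcome. A reader might also infer that the plan definitely ends follow-up. That holds only if 6.3 overrides 5.4, 5.10 and footnote i, and nothing says that it does.

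**Conclusion.** The conflict between 6.3 and 5.10 is real and unresolved. Followed as written, 6.3 censors global PFS early for reasons that are often related to tolerability and may differ by arm. The effect on overall survival is less certain, since it arises only if 6.3 also displaces 5.9 and footnote j.

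The size cannot be fixed from the documents. At assumed removal of 14%/5% to 25%/10% (INT/INP), concentrated in patients who would progress, a nominal 0.05 false-positive rate in favour of INT becomes about 0.06 to 0.09, and a nominal 0.10 becomes about 0.12 to 0.17. If removal is unrelated to prognosis, the cost is 0 to 5 points of power. These results rest on assumed rates and timing and on a log-rank test in place of the cure model.

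A reader might take 0.640 against 0.60 as a 4-point false gain for INT. That figure needs no removals at all in INP and a poor prognosis in those removed. The documents establish neither, and other plausible inputs shrink or reverse it. The point is worth correcting because the change is small and lost outcomes cannot be repaired later.

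**What to change.** Reconcile the wording in 6.3 and 5.3 with 5.8, 5.10, 6.4, the permanent-discontinuation text in 6.3 and footnote i, so that stopping troriluzole/placebo is not a reason to leave the study. Keep 5.10 as the only off-study list. How long the drug may be held, and which other protocol therapy continues, are for the sponsor to reconcile; no view is taken on either.

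Add an explicit statement, since 5.9 and footnote i do not supply it. Every randomized patient who stops study drug without progression continues the calendar's brain MRI and CT assessments until progression or death, and survival follow-up for 3 years.

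The cost is a few sentences in an amendment, plus scans and visits, most of them already in the calendar, for a limited number of patients. At the assumed rates that is at most about 9 (45 × 0.14 + 45 × 0.05 = 8.55) to 16 (45 × 0.25 + 45 × 0.10 = 15.75) of the 90 randomized.

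### Section 6.3: an unqualified one-level restart rule contradicts the section's own rules for grade 4 events and for short grade 1 and non-DLT grade 2 holds

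*Combined protocol and SAP*

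**What the plan says.** Protocol section 6.3 opens its holding criteria with "Troriluzole vs. placebo will be omitted and dose reduced for related AEs as follows" and then gives a rule for each grade:

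- **Grade 1.** If the patient cannot tolerate the event, "the drug may be held for 1 week at a time without lowering the dose". A hold of more than 1 week costs one level.
- **Grade 2.** If drug resumes within 1 week, "drug will be continued at the same dose, or, at the discretion of the treating investigator, it may be dose-reduced". A hold of more than 1 week costs one level, and so does a grade 2 event that meets the DLT criteria of section 6.2.
- **Grade 3.** One level on resumption.
- **Grade 4.** "If the patient is able to resume drug, drug will be dose-reduced two levels".

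The next subsection, on troriluzole and placebo dose reductions, comes immediately before the dose-level table and states: "When therapy resumes, the dose must be reduced by one level per the table below". It names no grade or hold duration and does not refer back to the rules above it. The sentence after it limits the number of reductions to 2.

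**The concern.** A site cannot follow both the general sentence and the grade rules in every case. The sentence is mandatory in tone and sits directly above the table that staff would consult to look up a restart dose.

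The case that matters most is a related grade 4 event in a patient at level 0. Following the general sentence there restarts the patient at a higher dose than the grade 4 rule sets. Level 0 is the dose that the phase Ib study with nivolumab identified as the MTD (section 2.4), and section 7.1 describes several toxicities of the parent drug as dose related, so the size of the step down has clinical meaning.

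After a short grade 1 or grade 2 hold the error runs the other way, toward a reduction that the grade rule does not require.

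**Working it through.** There is no planned figure to reproduce. The check sets each grade rule beside the general sentence, using the dose table in section 6.3.

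**Daily dose at each level**

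- Level 0: 140 + 280 = 420 mg
- Level -1: 140 × 2 = 280 mg
- Level -2: 140 mg

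**Restart dose from level 0**

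| Related event and hold | Grade rule | General sentence | Result |
|---|---|---|---|
| Grade 1, up to 1 week | 420 mg/day | 280 mg/day | conflict |
| Grade 1, over 1 week | 280 | 280 | agree |
| Grade 2, not DLT, up to 1 week | 420, reduction optional | 280, mandatory | conflict |
| Grade 2, over 1 week | 280 | 280 | agree |
| Grade 2, meets DLT criteria | 280 | 280 | agree |
| Grade 3 | 280 | 280 | agree |
| Grade 4 | 140 | 280 | conflict |

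**Size of the conflicts**

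- Grade 4 from level 0: 280 / 140 = 2.0, so the general sentence gives twice the dose.
- Short grade 1 or non-DLT grade 2 hold from level 0: (420 - 280) / 420 = 33% below the allowed dose.
- The same hold from level -1: (280 - 140) / 280 = 50% below the allowed dose.

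No dose difference is computed for grade 4 from level -1. Two levels down from there leaves the table, and the text does not settle whether level -2 is a floor.

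**Does any other text resolve it?** Section 6.3 has one tie-breaker, which picks the lowest dose. Its condition is "If a participant experiences multiple adverse events and there are conflicting recommendations", so it does not cover two rules that apply to one event. If stretched to do so, it would give the intended answer for grade 4 but would override the same-dose provisions for short grade 1 and grade 2 holds. The lead-in to the holding criteria introduces the grade rules but does not rank them above the later sentence.

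**The case against.** The strongest reply is that ordinary reading settles the matter. The grade rules are specific, and the general sentence can be taken as merely naming the step unit of the table beneath it. Read literally, that sentence would leave the grade 4 rule and the short-hold provisions with nothing to do. This is very likely the intent. It stands as a reason to treat the point as minor, but it does not remove a mandatory instruction that no other sentence qualifies.

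The grade 4 risk also has real limits. The two-level rule is explicit, in bold, and closes the paragraph just above. Drug is held and the event reassessed until it is Grade 1 or lower. Permanent discontinuation is available. The physician may later re-escalate any reduced patient as far as the starting dose, so 280 mg/day is not permanently barred after grade 4; what is at issue is the first restart dose. Section 2.3 reports no grade 4 or 5 events in the phase 2 riluzole trial. That is limited reassurance, because the trial was small and riluzole was not combined with checkpoint inhibitors, whereas section 6.7 directs that shared toxicities usually be attributed to all three drugs. These limits stand.

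The short-hold conflict has little consequence. The extra reduction can be reversed by re-escalation, and for grade 2 the investigator may reduce anyway.

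A reader might infer two further conflicts that the documents do not support:

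- **Holds under section 6.1.** That section says "For AEs unrelated to study drug(s), therapy may be held/resumed at the discretion of the treating investigator" and "Dosing interruptions are permitted in the case of medical / surgical events or logistical reasons not related to study therapy", and states no dose reduction for either. But the reduction rules in 6.3 are introduced for related events only, so 6.1 handles these interruptions separately.
- **A patient already at level -2.** One could say the general sentence sends this patient below the table. The very next sentence caps reductions at 2, so no third reduction is available.

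**Conclusion.** The sentence is wrong as written. It contradicts the section's own rules in three situations and agrees with them in the other four. The consequence of most concern is a restart at 280 instead of 140 mg/day after a related grade 4 event at level 0. The others are a forced restart at 280 where 420 mg/day is allowed, or at 140 where 280 is allowed, after a grade 1 or non-DLT grade 2 hold of up to 1 week.

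This rests on a literal reading of the general sentence and on the dose levels in the table. It does not assume that sites will misread the section. The documents give no frequency for these events under this regimen, so none is claimed.

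The point is a minor inconsistency in a dosing rule and does not challenge a design choice. Sample size, power and the intention-to-treat primary analysis are unaffected. It is worth correcting because it concerns an operative dosing instruction.

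**What to change.** Replace the sentence in section 6.3 with:

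*When therapy resumes after a hold for a related AE, the dose is set by the grade-specific rules above (including hold duration, the grade 2 DLT criterion and investigator discretion where stated), using the levels in the table below.*

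The parenthesis is needed. A sentence tied only to grade and hold duration would lose the one-level reduction for grade 2 events that meet DLT criteria, and the investigator's option to reduce after a short grade 2 hold.

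The wording adds no new dosing or discontinuation rule. Whether level -2 is a floor or a stopping point remains for the sponsor to decide. The cost is one sentence, with no effect on sample size, visits or analysis.
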